6.12.1.1 Progressive Multifocal Leukoencephalopathy (PML)

A patient with multiple sclerosis developed PML after nearly 8 months of treatment with another S1P₁ agonist³¹, and enablement of the John Cunningham (JC) virus is therefore a potential adverse effect of this therapeutic class. Patients in this trial should therefore be monitored for any new onset or worsening of neurological signs and symptoms. Signs and symptoms associated with PML are diverse, progress over days to weeks, and include progressive weakness on one side of the body or clumsiness of limbs, disturbance of vision, and changes in thinking, memory, and orientation leading to confusion and personality changes. The progression of deficits usually leads to death or severe disability over weeks or months. If PML is suspected, withhold dosing and refer to a neurologist; if confirmed, discontinue dosing permanently.

The investigator or sub-investigator will administer the subjective PML checklist during screening to exclude patients with positive responses from enrolling into the study. The subjective PML checklist will be administered at each site visit (except D-1) to probe for symptoms suggestive of PML. Any patients reporting signs and/or symptoms of PML will undergo objective testing and must be referred to a neurologist for a full evaluation.

A copy of the PML checklist is provided in [Appendix 1](#).

6.12.2 Serious Adverse Events and Expedited Reporting of Adverse Events

An SAE is any untoward medical occurrence that at any dose results in the following outcomes:

- Death
- Is Life-Threatening
- Required/Prolonged Hospitalization
- Disability/Incapacity
- Congenital Anomaly/Birth Defect
- Important Medical Event

SAEs will be captured from the time of ICF signature to 30 days after the last dose of study drug, and will be monitored until resolution or stabilization.

An important medical event that may not result in death, be life-threatening, or require hospitalization may be considered a SAE when, based upon appropriate medical judgment, it may jeopardize the patient and may require medical or surgical intervention to prevent one of the outcomes listed in this definition. Examples of such a medical event includes allergic bronchospasm requiring intensive treatment in an emergency room or at

home, blood dyscrasias, or convulsions that do not result in in-patient hospitalization, or the development of drug dependency or drug abuse.

Elective hospitalization and/or surgery for clearly pre-existing conditions (for example a surgery that has been scheduled prior to the patient's entry into the study) will not be reported as a SAE. All other hospitalizations, including elective hospitalizations for any condition that was not pre-existing, will be reported as a SAE.

Any AE considered serious by the investigator or which meets SAE criteria must be reported to PPD Pharmacovigilance (PVG) within 24 hours from the time study site personnel first learn about the event.

The following contact information is to be used for SAE reporting:

EMEA ASIA Safety Central Mailbox: [REDACTED]
[REDACTED]

Or alternatively:

PPD Medical Affairs/Pharmacovigilance
PPD PVG Hotline: (United Kingdom number) [REDACTED]
PPD PVG Fax line: (United Kingdom number) [REDACTED]

A full description of every SAE will need to be provided to PPD PVG (this may be supported by source documentation such as laboratory reports or a discharge summary should the patient be hospitalized).

Other safety issues as defined in ICH Topic E2A, 21 code of federal regulations (CFR) §312.32, and EU Eudralex Volume 10 also qualify for expedited reporting. In these situations, the process will be as detailed for SAEs above:

- SAEs which could be associated with the trial procedures;
- SAEs and AEs of special interest that could materially influence the benefit-risk assessment of a medicinal product, such as: a clinically important increase in the rate of a serious suspected adverse reaction over that listed in the investigator brochure.

6.12.2.1 Patient and Patient-partner Pregnancy

Patients who become pregnant during the study will be discontinued immediately. Although not considered an SAE or AE, pregnancies occurring during the period of study drug administration (Day 1 to Week 12) until 30 days after the last dose of study drug should be reported to the sponsor contact and IEC in the same manner as an SAE.

Pregnancies will be followed every trimester through the first well baby visit. For female partners whom become pregnant by male study patients during the course of the study, reasonable efforts will be made to collect information on the partner's pregnancy through the first well baby visit as provided by the male study patient.

6.12.3 Assessment of Adverse Event Severity

The severity of each AE will be assessed at onset by a nurse and/or physician. When recording the outcome of the AE the maximum severity of the AE experienced will also be recorded. The severity of the AE will be graded according to the CTCAE v4.03³² definitions, listed below:

Grade 1: Mild; asymptomatic or mild symptoms; clinical or diagnostic observations only; intervention not indicated.

Grade 2: Moderate; minimal, local or noninvasive intervention indicated; limiting age-appropriate instrumental Activities of Daily Living (ADL)*.

Grade 3: Severe or medically significant but not immediately life-threatening; hospitalization or prolongation of hospitalization indicated; disabling; limiting self-care ADL**.

Grade 4: Life-threatening consequences; urgent intervention indicated.

Grade 5: Death related to AE.

Activities of Daily Living:

*Instrumental ADL refer to preparing meals, shopping for groceries or clothes, using the telephone, managing money, etc.

**Self-care ADL refer to bathing, dressing and undressing, feeding self, using the toilet, taking medications, and not bedridden.

6.12.4 Assessment of Adverse Event Relationship to Study Medication

The relationship of an AE to investigational product(s) will be classified using modified WHO criteria (Edwards and Biriell, WHO Collaborating Centre for International Drug Monitoring 1994) as follows:

Related: a clinical event, including laboratory test abnormality, with a reasonable time sequence to administration of the drug, unlikely to be attributed to concurrent disease or other drugs or chemicals, and which follows a clinically reasonable response on withdrawal. Re-challenge information is not required to fulfill this definition; or an event that could also be explained by concurrent disease or other drugs or chemicals where information on drug withdrawal may be lacking or unclear.

Not related: a clinical event, including laboratory test abnormality, with sufficient evidence to accept that there is no causal relationship to drug administration (e.g., no temporal relationship to drug administration, because the drug was administered after onset of event; investigation shows that the drug was not administered; proof of other cause; etc.); or an event with a temporal relationship to drug administration which makes a causal relationship improbable, and in which other drugs, chemicals or underlying disease provide plausible explanations.

6.12.5 Assessment of Adverse Event Outcome

Outcome of AEs will be defined according to ICH Topic E2B, ICH Guideline.

- Recovered/Resolved
- Recovered/Resolved with Sequelae
- Recovering/Resolving
- Not Recovered/Not Resolved
- Fatal
- Unknown

6.12.6 Action Taken for Adverse Event

Action taken for AEs will be documented according to the following:

- Concomitant medication or other treatment
- Withdrawal from the study

6.12.7 Action Taken for Study Drug

Any action taken with study drug will be defined according to ICH Topic E2B, ICH Guideline and documented in the CRF according to the following:

- Drug Withdrawn
- None (not changed)
- Dose Interrupted
- Unknown
- Not Applicable

6.12.8 Follow-up of Adverse Events Present at Last Scheduled Study Visit

AEs present at the last study day (Week 12) that require follow-up or a repeat laboratory test will be followed-up according to the site's standard practice for AE follow-up.

6.13 Concomitant Medications and Procedures

All medications (over the counter [OTC] and prescribed) that are taken by patients and all procedures that are performed during the screening period and during the study must be recorded in the case report form (CRF) with start date/time and stop date/time, if known.

The following should be taken into account with regard to concomitant procedures:

- Patients may not undergo major elective surgery while enrolled in this study.
- Patients may not donate sperm, or oocytes during the study and for 30 days after the last dose of study drug.

6.13.1 Permitted medications for the treatment of pyoderma gangrenosum and associated conditions

The following concomitant medication are allowed provided that the dose has been stable for at least 2 weeks prior to baseline and remain stable throughout the study:

- Oral corticosteroids (maximal allowed prednisone ≤ 20 mg/day, or equivalent)
- TNF-alpha inhibitor (etanercept, infliximab, adalimumab or other)
- Oral 5-ASA medication (for patients with ulcerative colitis)
- Antidiarrheal treatment
- OTC analgesics (paracetamol / acetaminophen, NSAIDs)

In addition, topical medication (other than excluded medication) that the patient is receiving at baseline should be continued, provided that these are stable for 2 weeks prior to baseline and should remain stable throughout the study.

Only non-sticking dressing of the wounds (e.g., jelonet and compression bandages) could be used throughout the study period.

6.13.2 Excluded Medications

The following medications are excluded prior or during the study:

- Exposure to B-cell or T-cell targeted therapies (such as natalizumab, rituximab, abatacept) within 5 half-lives prior to Day 1
- Other immunosuppressive, immunomodulating or antineoplastic agents or other monoclonal antibody / biologic not listed in the Permitted Medications within 5-half-lives prior to Day 1 (small molecules) or 60 days prior to D1 (biologics).
- All live vaccines within 6 weeks prior to Day 1, during study treatment and for at least 6 months after the last dose of study drug
- Moderate to strong inhibitors of CYP2C9 (e.g., amiodarone, felbamate, fluconazole, miconazole, piperine). within 5-half-lives prior to Day 1, during the study and for 2 weeks after the last intake of study medication
- Other routes for systemic corticosteroids (IM and IV)
- Class Ia or Class III anti-arrhythmic agents
- Any other medication which in the opinion of the investigator would affect the suitability of the patient to continue in the study, interfere with interpretation of study results or affect compliance with the protocol requirements
- Receipt of any investigational agent within 30 days or 5 half-lives (whichever is longer), prior to Day 1.

6.14 Removal of Patients from the Trial or Study Drug

Patients experiencing a significant infection (as judged by the investigator) will be discontinued from the study drug immediately.

The study may be terminated early if, in the opinion of the sponsor, investigator, or IEC, an unacceptable risk to the safety and welfare of patients is posed by the continuation of the study in light of review of the key safety data.

Patients will be free to withdraw from the study at any time should they so wish. A patient may be withdrawn from the study for any of the following reasons (including but not limited to):

- Clinical investigator may remove a patient if, in his/her opinion, it is in the best interest of the patient.
- Withdrawal of consent - Any patient may withdraw his/her consent from the study at any time. The investigator should make a reasonable attempt to document the specific reason why consent was withdrawn.
- Deviation/noncompliance with the protocol or study drug (<80%).
- An AE.
- Lost to follow up.

6.14.1 Handling of Withdrawals

Although a patient is not obliged to give his/her reason for withdrawing prematurely, the investigator will make a reasonable effort to obtain the reason while fully respecting the patient's rights. If there is a medical reason for withdrawal, the patient will remain under the supervision of the study physician until in satisfactory health. Reasonable efforts will be made to contact a patient who fails to attend any follow-up appointments, in order to ensure that he/she is in satisfactory health.

If a patient is prematurely discontinued from this study, every attempt will be made to follow the Week 12 procedures. If consented by the patient, effort will be made to conduct a follow-up visit within 2 weeks of discontinuation [REDACTED] if the patient has received at least 1 dose of the study drug.

6.14.2 Replacements

Patients who terminate early from the study will not be replaced.

6.15 Study and Site Discontinuation

The Sponsor has the right to terminate this study at any time. Reasons for terminating the study may include, but are not limited to, the following:

- The incidence or severity of AEs in this or other studies indicates a potential health hazard to patients.
- Patient enrollment is unsatisfactory.

The Sponsor will notify the investigator if the study is placed on hold, or if the Sponsor decides to discontinue the study or development program.

The Sponsor has the right to replace a site at any time. Reasons for replacing a site may include, but are not limited to, the following:

- Excessively slow recruitment
- Poor protocol adherence
- Inaccurate or incomplete data recording
- Non-compliance with the ICH guidelines for GCP

7 DATA MANAGEMENT

7.1 Data Collection

All data (ECGs, clinical laboratory data, and all other study-related data) will be collected according to the sponsor/CRO's SOPs or according to study site standards, if applicable.

7.2 Data Coding

7.2.1 Adverse Events

AEs will be coded using the most current Medical Dictionary for Regulatory Activities (MedDRA) and tabulated, including categorical information of interest such as onset and resolution times, time of onset relative to dose, severity at onset, maximum severity, causal relationship to study medication, and action taken. Whenever possible, a constellation of signs and symptoms should be recorded as a unifying diagnosis (e.g., self-limited fever, runny nose, cough, and scratchy throat should be captured as an upper respiratory infection rather than by the individual signs and symptoms). AEs will be regarded as 'pre-treatment' if they occur between screening and the time of administration of the first dose of etrasimod. All other AEs that occur after the first dose of study medication will be considered to be 'treatment-emergent'.

7.2.2 Concomitant Medications and Non-Drug Treatments

Due to the variability in how medications are recorded, a standard naming convention is required in order to tabulate this data effectively. A common method of standardization is to categorize medications by their Preferred Term. In order to do this, medications will be coded using the World Health Organization Drug Dictionary (WHO DD), Format C.

7.2.3 Medical History

Medical history will be coded using the most current MedDRA-version.

8 PLANNED STATISTICAL METHODS

Details of the statistical analyses will be included in a separate statistical analysis plan (SAP) which will be finalized before database lock. If, after database lock, changes are made to the pre-specified SAP, the changes will be listed along with an explanation as to why they occurred in the Clinical Study Report.

Summary statistics will be provided to describe efficacy and safety measures. Confidence interval of key efficacy measures will be also produced for non-inferential comparisons with historical data.

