6.9.2 Physician Global Assessment for Active Skin Manifestations

The physician's global assessment for active skin manifestations will record the number of ulcers, target lesion noted for endpoint evaluation, diameters of each target lesion and score of evaluation at each visit. The scores range from 0 (total resolution) to 4 (no evidence of healing) ([Appendix 2](#)).

This assessment sheet will be completed by the investigator after evaluating the patient's disease as per [REDACTED]

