8.1.2 Hypotheses

There are no formal hypothesis tests specified in this open-label study due to the lack of control treatment group.

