8.3 Analysis Populations

Efficacy endpoints will be analyzed in enrolled patients who have baseline and at least 1 post-baseline measure.

Safety endpoints will be analyzed in enrolled patients who received at least 1 dose of the study drug.

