8.5 Efficacy Endpoints

As this is proof-of-concept study all endpoints will be exploratory. The efficacy endpoints will be as follows:

- change from baseline (Day 1 pre-dose) to Week 12 in Physician Global Assessments for active skin manifestations.

Assessment of target lesion/ulceration

- 0: Total resolution of target ulcer with no signs of active PG*
- 1: almost completely healed target ulcer with only minimal signs of active PG*
- 2: Evidence of target ulcer healing which involves at least 50% of ulcer/ulcer margin*
- 3: Evidence of target ulcer healing which involves less than 50% of ulcer/ulcer margin*
- 4: No evidence of target ulcer healing*

- change from baseline (Day 1 pre-dose) to Week 12 in Patient Global Assessments for active skin manifestations: Visual Analog Scale (VAS) for assessment of severity of the disease and severity of pain by patient.
- change from baseline (Day 1 pre-dose) to Week 12 in Dermatology Life Quality Index (DLQI) (to measure how much a patient's life is affected through their skin problems)
- change from baseline (Day 1 pre-dose) to Week 12 in CRP levels

In addition, the following measures will be assessed as per Schedule of Procedures and Visits:

- Imaging (digital photos) of the target lesion.
- Evaluation of the changes in surface area of target lesion.
- Skin punch biopsies (if performed).

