8.6 Statistical Methods

8.6.1 Efficacy Analysis

There are no inferential comparisons for study endpoints. Summary statistical analyses will be performed for all efficacy measures. For proportion based measures, N, frequencies, proportion and its 95% confidence interval (CI) will be produced. For continuous measure, N, mean, median, range, and SD will be produced for observed values, and additional 95% CI for change or percent change from baseline will be produced if applicable.

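### Should the SAP be finalised before dosing because the protocol names no responder, key measure or Week 12 rule?

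*Combined protocol and SAP*

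**What the plan says.** Section 8 (Planned Statistical Methods) delegates the detail: "Details of the statistical analyses will be included in a separate statistical analysis plan (SAP) which will be finalized before database lock". It adds a safeguard for later changes: "If, after database lock, changes are made to the pre-specified SAP, the changes will be listed along with an explanation". It also announces the use to be made of the intervals: "Confidence interval of key efficacy measures will be also produced for non-inferential comparisons with historical data".

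Section 8.6.1 covers proportions in general terms: "For proportion based measures, N, frequencies, proportion and its 95% confidence interval (CI) will be produced". Continuous measures get N, mean, median, range and SD of observed values, with a 95% CI for change where applicable.

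Section 8.5 lists changes to Week 12, all labelled exploratory. The first is "change from baseline (Day 1 pre-dose) to Week 12 in Physician Global Assessments for active skin manifestations"; the others are the patient VAS scores, DLQI and CRP. None is a proportion and none is called key. The PGA has five ordered categories, 0 to 4, with no responder cut.

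Section 8.3 fixes the efficacy set: "Efficacy endpoints will be analyzed in enrolled patients who have baseline and at least 1 post-baseline measure". Sections 3.1 and 6.14.1 ask for the Week 12 procedures when a patient stops early, and Section 6.14.2 rules out replacement. On inference, Section 8.1.2 says: "There are no formal hypothesis tests specified in this open-label study due to the lack of control treatment group".

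**The concern.** Three things are promised or implied but not defined: the key efficacy measures, any proportion built on the PGA, and the treatment of a patient with no Week 12 value. The study is open-label, and under Section 6.9.2 the investigator records "diameters of each target lesion and score of evaluation at each visit". If the SAP is still open late in the study, a cut-off or key measure could be chosen with the outcomes of all 8 patients in view. The duty in Section 8 to list and explain changes starts only after lock, so it does not reach choices made before then.

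At stake is the credibility of the descriptive evidence for proof of concept, including any proportion set beside historical data. With 8 patients, one reclassified patient moves a proportion noticeably, so a rule chosen to fit the data could flatter the result.

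**Working it through.** **What the plan's own figure allows.** Section 8.2 gives N = 8 and says there was no formal calculation. No alpha, power, response rate or SD is stated, so there is nothing to reproduce. All counts below are illustrative assumptions, not trial data.

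**Formula.** Exact (Clopper-Pearson) 95% interval for x of n: lower limit = 2.5% quantile of Beta(x, n − x + 1); upper limit = 97.5% quantile of Beta(x + 1, n − x). One patient of 8 is 1/8 = 12.5 points.

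**Cut-off.** Assume Week 12 PGA scores 0, 1, 2, 2, 3, 3, 4, 4.

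| Responder cut | Rate | Exact 95% CI |
|---|---|---|
| PGA 0–1 | 2/8 = 25.0% | 3.2 to 65.1 |
| PGA 0–2 | 4/8 = 50.0% | 15.7 to 84.3 |

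**Week 12 handling.** Assume 8 dosed patients, 7 with a Week 12 visit and 1 with only an early-termination value. That patient stays in the Section 8.3 set.

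| Rule | Early value meets the cut, 2 of the other 7 do | Early value does not, 3 of the other 7 do |
|---|---|---|
| Counts as Week 12 | 3/8 = 37.5% (8.5 to 75.5) | 3/8 = 37.5% (8.5 to 75.5) |
| Kept at its actual week, missing Week 12 = non-response | 2/8 = 25.0% (3.2 to 65.1) | 3/8 = 37.5% (8.5 to 75.5) |
| Observed cases at Week 12 | 2/7 = 28.6% (3.7 to 71.0) | 3/7 = 42.9% (9.9 to 81.6) |

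No rule is uniformly the more favourable; the direction depends on the patient.

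**Endpoints actually planned.** For a mean change, the t-based 95% half-width is t(0.975, n − 1)/√n in SD units: 0.84 SD at n = 8 and 1.05 SD at n = 6. Section 8.6.1 already requires N with each continuous summary, so a loss of Week 12 values would be visible to the reader.

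**Setting the sections side by side.**

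- *Fixed in the protocol:* the measures, baseline (Day 1 pre-dose), Week 12, the efficacy set, the 95% level and the absence of tests. Section 1.2 requires a formal written amendment to change protocol content.
- *Left to the SAP:* the choice of key measures, any PGA cut, the CI method and the handling of early-termination values.
- *No such endpoint:* the two tables above need a responder endpoint, which Section 8.5 does not contain. Tabulating the five PGA categories with their proportions satisfies Section 8.6.1 without any cut.

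**The case for a change.** The strongest case for a change is that the remedy costs only wording. Finalising the SAP before first dosing, naming the key measures and any cut, and stating the Week 12 rule would need no patients, visits or data. A rule fixed before results exist cannot be suspected of having been fitted to them. The SAP may well settle the details, but the protocol does not require it to do so before outcomes are visible.

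Part of this stands. The gaps in the protocol text are real, and Sections 8.3 to 8.6.1 show no redaction that would explain them. The early-discontinuation visit is a data-collection rule, not an analysis rule. The amendment requirement in Section 1.2 would not stop a responder cut from being introduced in the SAP. Earlier finalisation would be reasonable.

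The specific remedies are weaker:

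- An all-dosed denominator with missing counted as non-response is one defensible convention. It would displace the Section 8.3 set for an endpoint the protocol does not define. The exclusion it corrects, a dosed patient with no post-baseline measure, is unlikely given the Week 2 visit and the early-termination procedures.
- Asking for exact intervals answers a method nobody proposes. At 0/8 a Wald interval collapses to 0 to 0 against an exact 0 to 36.9, and an analyst with 8 patients can be expected to see that.
- Reporting early-termination values at their actual week needs visit windows between Weeks 2, 4, 8 and 12, which would themselves have to be chosen.
- Section 10.3 describes checking that records are complete and follow the protocol. It does not show that those writing the SAP review efficacy results. The visibility point rests on the open-label design alone.

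**Conclusion.** No change to the plan is called for. This is detail that the protocol expressly hands to a separate SAP, with a deadline that is common practice and is a latest date, not evidence of late drafting. In illustration, the open choices can move a proportion by 12.5 to 25 points. That movement applies to a responder rate the protocol does not plan, within exact intervals more than 60 points wide (65.1 − 3.2 = 61.9; 84.3 − 15.7 = 68.6). Wide intervals do not excuse a data-driven cut. They do mean that either figure would be read as a rough description.

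No test, error rate or stated go/no-go threshold depends on the choice, and no bias is shown. This conclusion rests on two assumptions: that the SAP, which was not available, handles the key measures and Week 12 values in the usual way, and that the historical comparison stays non-inferential, as Section 8 says. If a PGA responder rate were later presented as the main evidence of efficacy, the date on which its definition was fixed would matter and should be checked in the study report.
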